6.3 CLINICAL EXPERIENCE

[Redacted text block]

[REDACTED]	[REDACTED]	[REDACTED]
[REDACTED]	[REDACTED]	[REDACTED]
[REDACTED]	[REDACTED]	[REDACTED]
[REDACTED]	[REDACTED]	[REDACTED]

[REDACTED]

Additional details for each study are available in the IB.

6.4 STUDY DRUG DOSE RATIONALE

In this study, study drug is defined as oral nafithromycin tablet or oral moxifloxacin capsule (i.e., over-encapsulated tablet). Relevant matching placebo formulations (tablets and capsules) are used to maintain the blind.

6.4.1 Nafithromycin

Rationale for 800 mg of nafithromycin once daily for 3 – 5 days:

[REDACTED]

[REDACTED]

[REDACTED]

[REDACTED]

6.4.2 Moxifloxacin

Moxifloxacin was selected as the optimal comparator for this Phase II CABP study, given its long history of efficacy and tolerability in this infection. The proposed dose regimen and treatment scheme (400 mg once daily for 7 days) has been selected for consistency purposes worldwide as this study is planned to be conducted in different regions, such as Europe, US and South Africa.

Moxifloxacin has a similar spectrum of activity to that of nafcithromycin, with coverage against the most common typical and atypical causes of CABP (e.g., *S. pneumoniae* [including penicillin-resistant and macrolide-resistant isolates], *H. influenzae*, *Mycoplasma pneumoniae*, *Chlamydia pneumoniae*, and *Legionella pneumophila*). This broad spectrum of activity along with its once-daily dosage allows for the double-blind monotherapy design of this trial, obviating the need for combination therapy in either treatment arm. The use of moxifloxacin for CABP is consistent with the current treatment guidelines by IDSA/ATS and ESCMID ([Mandell, 2007](#); [Woodhead, 2005](#)). In conclusion, the 7-day oral treatment duration of moxifloxacin, allowed in this study was selected to be generally consistent with clinical guideline recommendations as well as the duration of therapy recommended in the package inserts for the oral switch agent (moxifloxacin package inserts) from different regions, and can thus be considered a globally appropriate treatment duration from both efficacy and safety standpoints.

7.0 STUDY OBJECTIVES

7.1 PRIMARY OBJECTIVES

The primary objectives of this study are:

- To assess the overall safety and tolerability of oral nafithromycin
- To assess the clinical response in the ITT population at Day 4

7.2 SECONDARY OBJECTIVES

The secondary objectives of this study are:

- To assess the clinical response in the micro-ITT population at Day 4
- To assess the clinical outcome in the ITT and CE populations at EOT and TOC
- To assess early improvement in clinical symptoms and normalization of vital signs in the ITT population at Day 4
- To assess clinical outcome in micro-ITT population at TOC
- To assess by-subject and by-pathogen microbiological response in micro-ITT and ME populations at TOC
- To assess readmission to the hospital (or admission to the hospital if not previously hospitalized) for any reason prior to FU

7.3 EXPLORATORY OBJECTIVES

Additional exploratory and subgroup analyses may be conducted, as described in the Statistical Analysis Plan.

8.0 STUDY DESIGN

8.1 TYPE OF STUDY

This is a Phase II prospective, multicenter, multinational, randomized (1:1:1), double-blind, comparative study to determine the efficacy, safety, tolerability, and PK of oral nafithromycin versus oral moxifloxacin for treatment of adults with CABP. Study drug is defined as oral nafithromycin tablets or oral moxifloxacin capsules. Relevant matching placebo formulations (tablets and capsules) are used to maintain the blind.

Subjects providing informed consent and meeting all study eligibility criteria will be randomized into the study in a 1:1:1 ratio to either of the following 3 treatment arms:

- Arm A: Nafithromycin 800 mg (two 400 mg tablets) PO q24h for 3 days; subjects will receive matching placebo (two nafithromycin placebo tablets PO q24h) on Days 4 through Day 7, and one moxifloxacin placebo capsule PO q24h on Days 1 through 7, to maintain the blind
- Arm B: Nafithromycin 800 mg (two 400 mg tablets) PO q24h for 5 days; subjects will receive matching placebo (two nafithromycin placebo tablets PO q24h) on Day 6 and Day 7, and one moxifloxacin placebo capsule PO q24h on Days 1 through 7, to maintain the blind
- Arm C: Moxifloxacin 400 mg (one 400 mg over-encapsulated tablet) PO q24h for 7 days; subjects will also receive two nafithromycin placebo tablets PO q24h on Days 1 through Day 7, to maintain the blind

Baseline assessments for study eligibility will occur within 24 h prior to randomization using IXRS, stratified by region (US vs. ex-US) and PORT Risk Class (II vs. III/IV), will be used to assign subjects (1:1:1) to Arm A, Arm B or Arm C. Study Day 1 is defined as the day that the study drug is first administered, and subsequent study days are defined by the number of consecutive calendar days thereafter.

Subjects may be treated in the study as inpatients or outpatients based on their clinical condition, at the discretion of the Investigator; however, only oral study drug will be administered (i.e., parental moxifloxacin will not be administered). Subjects will be assessed daily by the Investigator between Day 1 and Day 5, whether being treated for CABP in the inpatient or outpatient setting. Investigators will assess for clinical outcome on EOT (Day 7) and TOC (Day 15 ± 3 days). Vital signs, physical exam, assessment of CABP symptom severity, and other study procedures are detailed in [Table 3-1](#). A FU visit will be conducted on Day 31 ±3 days from the start of treatment. The FU visit may be conducted via telephone contact or by another interactive technology for subjects who were considered to be clinical successes and had no AEs or clinically significant laboratory or ECG abnormalities noted at or after the TOC visit; otherwise, the visit must be conducted in person.

8.2 RANDOMIZATION

Block randomization using an IXRS, stratified by region (US vs. ex-US) and PORT Risk Class (II vs. III/IV), will be used to assign subjects (1:1:1) to Arm A, Arm B or Arm C.

After informed consent has been obtained and study eligibility established, a study pharmacist or designee will obtain the study drug assignment from the IXRS. Subjects are considered randomized when the pharmacist or designee receives the IXRS-generated treatment assignment.

8.3 NUMBER OF SUBJECTS

Approximately 225 adult subjects (75 subjects per arm) diagnosed with CABP will be enrolled in this study.

Enrolment of PORT Risk Class II (PORT score 51 to 70; [Appendix II](#)) will be capped at 50% and enrolment of subjects with allowed prior systemic antibiotic use ([Appendix I](#)) will be capped initially at 25% (subject to change during study conduct).

8.4 EXPECTED DURATION OF SUBJECT PARTICIPATION

Each subject will remain in the study for approximately one month. This will include a Screening visit (within 24 h of randomization), a 7-day oral treatment period, and post treatment assessments at TOC (Day 12 to Day 18) and FU (Day 28 to Day 34).

9.0 SELECTION, DISCONTINUATION, AND WITHDRAWAL OF SUBJECTS

9.1 STUDY POPULATION

Adult subjects (≥ 18 years) with CABP will be enrolled in this study. Based on recent Phase III CABP study experience, subjects of at least 65 years of age will constitute approximately 48% of randomized subjects ([File, 2010a](#)).

9.2 INCLUSION CRITERIA

Subjects are required to meet all of the following inclusion criteria:

1. Male or female ≥ 18 years of age
2. Willing to participate in the study and provide written informed consent before any protocol specific assessment is performed
3. Meet the following clinical criteria for CABP:
 - a. Have at least TWO of the following symptoms (new or worsening):
 - Dyspnea (shortness of breath)
 - Cough
 - Production of purulent sputum
 - Pleuritic chest pain
 - b. Have at least TWO of the following vital sign abnormalities:
 - Fever or hypothermia documented by the Investigator (oral, rectal, or tympanic temperature $> 38.0^{\circ}\text{C}$ [100.4°F] or $< 36.0^{\circ}\text{C}$ [95.5°F])
 - Hypotension, defined as systolic blood pressure < 90 mm Hg
 - Tachycardia, defined as heart rate > 90 beats per minute
 - Tachypnea, defined as respiratory rate > 20 breaths per minute
 - c. Have at least ONE of the following laboratory abnormalities:
 - Hypoxemia defined as arterial oxygen saturation $< 90\%$ by pulse oximetry or $\text{PaO}_2 < 60$ mm Hg by ABG
 - Auscultatory findings on pulmonary examination consistent with bacterial pneumonia or pulmonary consolidation (e.g., rales, dullness on percussion, bronchial breath sounds, or egophony)
 - Elevated total WBC count ($> 10,000$ cells/ mm^3) or leucopenia (WBC $< 4,000$ cells/ mm^3)
 - Elevated immature neutrophils ($> 15\%$ band forms), regardless of total peripheral WBC count
 - d. Radiographic evidence of CABP:

- Radiographically-confirmed pneumonia, i.e., new or progressive pulmonary infiltrate(s) on CXR or CT scan consistent with acute bacterial pneumonia within 48 h prior to randomization
- e. PORT score of 51 to 105 (PORT Risk Class of II, III or IV) ([Appendix II](#))
4. All females must have a negative urine or serum pregnancy test (β -HCG) at Screening AND agree to the use of one of the following acceptable methods of contraception from Screening through TOC: surgical sterilization (defined as bilateral oophorectomy or bilateral salpingectomy, but excluding bilateral tubal occlusion), post-menopausal (defined by amenorrhea for at least 12 months following cessation of all exogenous hormonal treatments), barrier contraception (e.g., condom, intrauterine device), levonorgestrel intrauterine system (e.g., Mirena[®]), regular medroxyprogesterone injections (e.g., Depo-Provera[®]), sexual intercourse with only vasectomised partners, or abstinence. Note that oral contraceptives should not be used as the sole method of birth control because the effect of nafithromycin on the efficacy of oral contraceptives has not yet been established; subjects who take oral contraceptives must also use one of the acceptable forms of birth control (listed above) from Screening through TOC. Males must agree to use an acceptable barrier method of birth control (i.e., condom) with female partner(s) and must not donate sperm from Screening through TOC.
 5. Ability to ingest oral study drug (e.g., able to swallow large capsules intact, and no significant nausea, vomiting, diarrhea, or any other condition that might impair ingestion or absorption of oral study drug)

9.3 EXCLUSION CRITERIA

1. Subjects with any of the following confirmed or suspected types of pneumonia:
 - Aspiration pneumonia
 - HABP, defined as pneumonia with onset of clinical signs and symptoms after at least 48 h hospitalization in an acute in-subject health care facility.
 - HCAP, defined as pneumonia acquired in a long-term care or subacute healthcare facility (e.g., nursing home) or pneumonia with onset after recent hospital discharge (within 90 days of current admission and previously hospitalized for \geq 48 h)
 - VABP, defined as pneumonia with onset of clinical signs and symptoms after at least 48 h endotracheal intubation
 - Pneumonia that may be caused by pathogen(s) resistant to either study drug (nafithromycin or moxifloxacin), including viral, mycobacterial, or fungal pneumonia (e.g., *Pneumocystis jiroveci* pneumonia, active pulmonary tuberculosis)
 - Post-obstructive pneumonia
 - Pneumonia associated with cystic fibrosis

2. Suspected or confirmed pleural empyema (a parapneumonic pleural effusion is not an exclusion criterion) or lung abscess
3. Suspected or confirmed non-infectious causes of pulmonary infiltrates (e.g., pulmonary embolism, hypersensitivity pneumonia, congestive heart failure)
4. Receipt of 1 or more dose(s) of a potentially-effective systemic antibacterial treatment for treatment of the current CABP within 72 h prior to randomization with the exception of:
 - Receipt of a single dose of a short-acting antibacterial agent within 72 h of randomization ([Appendix I](#)), OR
 - Failure (worsening of symptoms) of at least 48 h of treatment for the current episode of CABP with an antibacterial agent other than a ketolide or fluoroquinolone
5. Subjects requiring concomitant adjunctive or additional potentially effective systemic antibacterial treatment for management of CABP
6. Evidence of significant immunologic disease determined by any of the following:
 - Current or anticipated neutropenia defined as < 500 neutrophils/mm³
 - Known infection with HIV (prior to Screening) and a CD4 count that is unknown or documented to be < 200 cells/mm³ within the last year, or an AIDS-defining illness; note that neither HIV nor CD4 testing is required at Screening
 - History of heart, lung, or kidney transplant
 - The receipt of cancer chemotherapy, radiotherapy, or potent, non-corticosteroid immunosuppressant drugs (e.g., cyclosporine, azathioprine, tacrolimus, immune-modulating monoclonal antibody therapy) within the past 3 months, or the receipt of corticosteroids equivalent to or greater than 40 mg of prednisone per day for more than 14 days in the 30 days prior to randomization
7. Known or suspected primary or metastatic neoplastic lung disease, bronchiectasis, bronchial obstruction, chronic neurological disorder preventing clearance of pulmonary secretions, or severe COPD (severe COPD is defined as known [prior to Screening] FEV₁/FVC < 0.70 and FEV₁ $< 50\%$ normal); note that pulmonary function tests are not required at Screening
8. Compromised hepatic or renal function, including but not limited to: clinical evidence of end-stage liver disease (e.g., ascites, hepatic encephalopathy), screening serum total bilirubin > 2 times ULN (unless associated with an elevated indirect bilirubin typical of Gilbert syndrome), AST or ALT > 3 times ULN, serum creatinine > 2.0 mg/dl and/or BUN > 30 mg/dl. Other clinically-significant abnormal laboratory findings should be discussed with the Medical Monitor prior to the subject's entry.
9. History of *Clostridium difficile*-associated disease within 6 months prior to enrolment

10. History of hypersensitivity, known contraindication (e.g. lactose intolerance, lactase deficiency and glucose-galactose malabsorption etc.) or allergic reaction (e.g., anaphylaxis, urticaria, other significant reaction) to any ketolide, any fluoroquinolone antibiotic medicinal products or any of their excipients.
11. Current second- or third- degree atrioventricular block or sick sinus syndrome, uncontrolled atrial fibrillation, severe or unstable angina, congestive heart failure, myocardial infarction within 3 months of the Screening visit, clinically significant ECG abnormalities including QTcF > 450 msec (males) or > 470 msec (females), or requirement for medications known to cause QT prolongation
12. Prior (within 14 days prior to randomization) or concomitant use of cytochrome P450 liver enzyme inducers (e.g., phenobarbital, carbamazepine, griseofulvin, sulfonyleureas, phenytoin, or rifampin)
13. History of tendon rupture
14. Current peripheral neuropathy or myasthenia gravis
15. Known or suspected seizure disorder or other CNS disorders that may predispose the subject to seizures or lower the seizure threshold
16. Nursing mother or pregnant female
17. Subjects who received any experimental drug within 30 days prior to enrolment
18. Require admission to in intensive care unit for any reason, life expectancy of less than 2 months, or any concomitant condition that, in the opinion of the Investigator, is likely to interfere with evaluation of the response of the infection under study, determination of AEs, or completion of the expected course of treatment

9.4 CRITERIA FOR PREMATURE DISCONTINUATION OF STUDY DRUG OR SUBJECT WITHDRAWAL FROM STUDY

Subjects should be encouraged to complete all study assessments. However, subjects may discontinue study drug or withdraw consent to participate in this study at any time without penalty or loss of benefits to which the subject is otherwise entitled.

9.4.1 Premature Discontinuation from Study Drug Administration

9.4.1.1 Discontinuations Due to Safety

Possible reasons for premature discontinuation from study drug administration due to safety include, but are not limited to, the following:

- Occurrence of an AE that, in the opinion of the Investigator, warrants the subject's permanent discontinuation from study drug administration.
- Meets Hy's law criteria, defined by at least 3-fold elevations of ALT or AST above the ULN, elevation of serum total bilirubin to > 2 times ULN without elevated serum alkaline phosphatase, and no other disease or condition can be found to explain the liver test abnormalities

- Known pregnancy or breastfeeding during the study drug administration period. Female subjects whose pregnancy test is positive post-baseline must be followed through the immediate postnatal period or until termination of the pregnancy. Study center personnel must report every pregnancy as soon as possible (within 24 h of learning of the pregnancy, as described in [Section 14.1.6](#)).

Assessments and Procedures: Subjects who are prematurely discontinued from study drug administration (i.e., before the anticipated full course of study drug required for effective treatment of the CABP) for safety reasons should continue to undergo study assessments at every study visit ([Section 11.0](#)). If a subject is discontinued from study drug on Day 3 or Day 4, an attempt should be made to collect any remaining PK blood samples scheduled for that day.

Clinical Outcome Assessment: Subjects prematurely discontinued from any study drug for safety reasons and for whom further antibacterial therapy is not required for treatment of the primary infection (i.e., the CABP has resolved completely or improved to the point where no further antibacterial therapy is necessary), may be assessed as a clinical cure at the EOT and TOC visits.

Subjects prematurely discontinued from any study drug for safety reasons and who require further antibacterial therapy for the CABP should be assessed as a clinical failure on the day of discontinuation and automatically assigned an outcome of clinical failure at the next outcome evaluation time point.

9.4.1.2 *Discontinuations Due to Insufficient Therapeutic Effect*

Possible reasons for discontinuation from study drug due to insufficient therapeutic effect include, but are not limited to, the following:

- Clinical worsening: Subjects who show systemic or local signs of clinical worsening may be prematurely discontinued from study drug administration at any time. If the Investigator deems the benefit-to-risk ratio of study drug continuance acceptable, study drug administration of at least 48 h is encouraged before discontinuation from study drug therapy.
- Lack of clinical progress: For subjects who are stable, yet do not show signs of improvement, the Investigator is encouraged to continue study drug therapy for at least 48 h before such subjects are considered clinical failures and prematurely discontinued from study drug therapy.

Assessments and Procedures: Subjects who are prematurely discontinued from study drug due to insufficient therapeutic effect should have EOT assessments conducted ([Section 11.8](#)) on the day of discontinuation and undergo safety assessments at TOC ([Section 11.9](#)). Prematurely discontinued subjects should also be encouraged to attend the FU visit. If a subject is discontinued from study drug on Day 3 or Day 4, an attempt should be made to collect any remaining PK blood samples scheduled for that day. If a subject is discontinued from study drug administration due to insufficient therapeutic effect and is switched to an alternative antibiotic, that therapy should be documented.

Clinical Outcome Assessment: Subjects who are prematurely discontinued from study drug administration due to insufficient therapeutic effect should be assessed as clinical failure on the day of discontinuation. Subjects prematurely discontinued from study drug administration due to insufficient therapeutic effect will be automatically assigned an outcome of clinical failure at the next outcome evaluation time point.

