9.7 GUIDANCE TO INVESTIGATORS ON WHEN TO END STUDY DRUG THERAPY

The duration of study drug in this study is a fixed 7-day course in all three Treatment Arms; therefore, subjects who are improving clinically will receive no less or no more than 7 days of the study treatment regimen. At Day 7 (EOT), an assessment of clinical outcome will be performed by the Investigator. A subject will be determined as a clinical cure at EOT if the subject is alive and the infection is sufficiently resolved such that further antibacterial therapy is not needed ([Section 13.2.2](#)). Note that subjects with CABP may have some residual findings related to infection (i.e., cough) requiring non-antibiotic ancillary treatment (e.g., expectorant) at EOT and still meet criteria for clinical cure.

If additional antibacterial therapy is required for the index CABP (e.g., progressively worsening CABP between Day 1 and Day 7, or gradually improving CABP that requires additional antibacterial therapy beyond 7 days), study drug should be discontinued, the subject will be deemed a clinical failure on the day of study drug discontinuation, and open-label antibacterial therapy will be started at the discretion of the Investigator. Administration of blinded study drug will not be allowed beyond Day 7. In cases of premature discontinuation of study drug, subjects should not be discontinued from the study itself; subjects should remain in the study and undergo all scheduled assessments at EOT, TOC and FU ([Section 11.0](#)).

The Investigator may use culture and susceptibility results from the local microbiology laboratory to help guide therapy; however, decisions to continue or discontinue study drug should be based on clinical response rather than susceptibility results (as nafithromycin susceptibility testing is not available at the local site). If the index CABP is caused by a microorganism that is not susceptible to fluoroquinolones, macrolides, or ketolides in vitro, the decision to continue or discontinue study treatment should be based on the subject's clinical course and the Investigator's clinical judgment. These cases should be discussed with the Medical Monitor prior to prematurely discontinuing study drug, and the rationale for this decision should be recorded in the source documents.

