11.10 FOLLOW-UP (FU)

FU is to be conducted on Day 31 \pm 3 days. The FU assessment may be conducted via telephone contact or by another interactive technology for subjects who were considered to be Clinical Successes and had no AEs or clinically significant laboratory or ECG abnormalities noted at or after the TOC visit; otherwise, the visit must be conducted in person.

Clinical Assessments:

- Assess for clinical relapse or recurrence of CABP, including new hospitalization for any reason within 30 days from initiation of treatment (a secondary endpoint, see [Section 13.2.4](#))
- Obtain a 12-lead ECG only if prior ECG(s) showed any clinically-significant abnormality
- Identify, assess and record any AEs

Central Laboratory Assessments:

- Obtain CBC, coagulation, and/or chemistry panel only if prior study laboratory results showed any clinically-significant abnormality ([Appendix IV](#)); previously-normal (or abnormal but not clinically-significant) laboratory tests do not need to be repeated.

Microbiological Assessments:

- If prior blood cultures are positive, repeated post-baseline blood cultures should be collected on the day that the positive blood culture is detected
- Repeated respiratory specimens should be obtained only if clinically indicated, e.g., if clinical relapse or recurrence of CABP

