13.2.4 Hospitalization Prior to the Follow-Up Visit

An assessment of hospitalization (defined as readmission to the hospital if previously hospitalized on or after study drug initiation [Day 1], or initial hospital admission (if not previously hospitalized) for any reason between the initiation of study drug (Day 1) and FU will be made programmatically based on information collected in the eCRF.

For the purposes of this secondary efficacy assessment, “hospital admission” is defined as inpatient admission for at least 24 h in an acute care facility (including inpatient hospital ward or emergency room); in contrast, admission to nursing homes, assisted living facilities, rehabilitation units, or acute care facilities (hospital wards or emergency rooms) for less than 24 h is not considered a formal hospital admission. The assessment of hospitalization within 30 days of study drug initiation is defined in [Table 13.2.4-1](#).

Of note, adverse events that lead to readmission or new admission to the hospital will meet SAE criteria, as defined in [Section 14.1.4](#).

Table 13.2.4-1 Hospitalization Prior to the Follow-Up Visit

Outcome	Definition
Hospitalization Prior to FU	Meets any of the following criteria: 
 • Hospital readmission for any reason between Day 1 and FU Visit, if previously hospitalized and discharged • Initial hospital admission for any reason between Day 2 and FU Visit, if not previously hospitalized on Day 1

Table 13.2.4-1 Hospitalization Prior to the Follow-Up Visit

Outcome	Definition
No Hospitalization Prior to FU	Does not meet the criteria for hospitalization within 30 days of study drug initiation as defined above, or till FU whichever is earlier.
Indeterminate	Study data are missing for evaluation of efficacy at FU Visit for any reason, including lost to follow-up.

Abbreviations: FU = Follow-Up

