14.1.4 Serious Adverse Events

An SAE is any adverse experience that occurs from the signing of the informed consent to the FU visit and that results in any of the following outcomes:

- Death
- Life-threatening situation (subject is at immediate risk of death)
- Inpatient hospitalization or prolongation of existing hospitalization
- Persistent or significant disability/incapacity
- Congenital anomaly/birth defect in the offspring of a subject who received study treatment
- Events that jeopardize the subject sufficiently that medical or surgical intervention may be required to prevent one of the above outcomes. Examples may include, but are not limited, to:

- Intensive treatment in an emergency room for allergic bronchospasm
- Blood dyscrasias that do not result in hospitalization
- Seizures that do not result in hospitalization

Progression of disease or insufficient therapeutic effect which causes new hospitalization (in subjects not previously hospitalized for the index CABP), rehospitalization (in subjects that were previously hospitalized for the index CABP and discharged) is not a SAE; however, if this leads to death, it should be recorded as a serious adverse event (SAE) ([Section 14.1.3](#))

The Sponsor is required to inform worldwide regulatory authorities of SAEs that meet specific criteria. Therefore, the Sponsor must be notified immediately regarding any SAE that occurs after informed consent is obtained. All SAEs and follow-up information must be reported within 1 business day, or 24 h as required by local regulations, by faxing a completed SAE Report Form to the fax number below (Table 14.1.4-1) or emailing a completed SAE Report Form to the [REDACTED] at [REDACTED].

Table 14.1.4-1: Toll-free Safety Line Numbers for SAE Reporting*

Country	Toll-free Safety Line Numbers
Bulgaria	[REDACTED]
Georgia	[REDACTED]
Latvia	[REDACTED]
Republic of South Africa	[REDACTED]
Romania	[REDACTED]
	[REDACTED]
Russia	[REDACTED]
	[REDACTED]
	[REDACTED]
USA	[REDACTED]
	[REDACTED]
	[REDACTED]

*Any fax sent to these lines will be routed to [REDACTED].

Supplemental information for each SAE should be submitted as soon as available and may include laboratory results, radiology reports, progress notes, hospital admission and emergency room notes, holding and observation notes, discharge summaries, autopsy reports, and death certificates.

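### Sections 9.4.1.2 and 9.7 set different follow-up after stopping for insufficient effect, which risks outcome-dependent gaps in hospitalization and convalescent serology data

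*Combined protocol and SAP*

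**What the plan says.** Three parts of protocol Section 9 set follow-up after study drug is stopped early.

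- **Section 9.4.1.2 (insufficient effect).** End-of-Therapy (EOT) assessments are done on the day of stopping; subjects then "undergo safety assessments at TOC". For FU: "Prematurely discontinued subjects should also be encouraged to attend the FU visit".
- **Section 9.7 (when to end study drug).** This covers subjects who need more antibacterial therapy, with progressive worsening as an example. It says "subjects should remain in the study and undergo all scheduled assessments at EOT, TOC and FU".
- **Section 9.4.1.1 (safety).** These subjects "should continue to undergo study assessments at every study visit".

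The opening of Section 9.4 says only "Subjects should be encouraged to complete all study assessments", which does not settle the matter.

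Two kinds of data depend on these visits. Section 11.10 lists under FU: "Assess for clinical relapse or recurrence of CABP, including new hospitalization for any reason within 30 days from initiation of treatment". In Section 13.2.4 hospitalization is Indeterminate when "Study data are missing for evaluation of efficacy at FU Visit for any reason, including lost to follow-up". Sections 11.9 and 12.4 place convalescent atypical serology at TOC, and Section 16.1.3 makes a serologic response one route into the micro-ITT population.

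**The concern.** Under 9.4.1.2 as written, follow-up depends on why a subject stopped, and it is thinnest for efficacy failures. They are plausibly the subjects most likely to be admitted, so gaps would be related to outcome.

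Safety reporting does not reliably fill the gap. Section 14.1.1 does not count progression, or an admission it causes, as an adverse event. Section 14.1.4 says such an admission "is not a SAE; however, if this leads to death" it is recorded as one. A non-fatal progression admission after TOC therefore has no assured route into the database if FU is missed.

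The stake for serology is population membership. If convalescent samples are taken less often from failures, entry to micro-ITT, and through it to ME, depends partly on an outcome after randomization. Micro-ITT is used for Day 4 response, TOC clinical outcome and microbiological response.

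**Working it through.** **The plan's one sample-size figure.** Section 16.2.1 gives a 95% interval of 66.9% to 86.7% for 78% of 75. Clopper-Pearson limits are the 0.025 quantile of Beta(x, n−x+1) and the 0.975 quantile of Beta(x+1, n−x). With n = 75 and x = 0.78 × 75 = 58.5 they are 66.94% and 86.75%, which agrees apart from the last digit. This point does not depend on that figure.

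**The requirements side by side.**

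| Reason for stopping | Section | TOC | FU |
|---|---|---|---|
| Safety | 9.4.1.1 | study assessments | study assessments |
| Insufficient effect | 9.4.1.2 | safety assessments | encouraged |
| Premature stop, including worsening | 9.7 | all scheduled | all scheduled |

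Rows two and three apply to the same subject when CABP worsens on treatment.

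**What could be lost, item by item.**

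1. *Clinical outcome at TOC:* nothing. Section 13.2.2 carries failure forward.
2. *Hospitalization:* Section 13.2.4 classifies this from the eCRF, and an admission already recorded counts whether or not FU takes place. Subjects under 9.4.1.2 are still seen at TOC (Day 12 to 18), although Section 11.9 lists no hospitalization item. The exposure is admissions the site has not recorded, mainly those after TOC, and non-admitted failures with no FU data.
3. *Convalescent serology:* Section 11.9 lists it with the other central laboratory draws, but Appendix IV omits it from the safety laboratory tests. A site asked for safety assessments could draw it or not.
4. *Micro-ITT and ME membership:* Section 16.1.3 also admits subjects by respiratory culture, blood culture or urinary antigen. Only those with serology as sole evidence are at risk. ME also requires the CE criteria of Section 16.1.4, including at least 80% of intended doses, so some early stoppers may be outside ME anyway.
5. *Microbiological response, once in the population:* failures without a culture are presumed persistence (Table 13.3.1-1), so this is not lost.

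**Illustration only.** The documents give no rate of stopping for insufficient effect, of admission, or of FU attendance. Let f be the share stopped, m the share of these with no FU data, h the admission rate among them, and 2% the admission rate in everyone else. Let r be the share of admissions among those without FU data that are already in the eCRF. All values are assumptions.

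- Subjects without FU data per arm = 75 × f × m. For f from 5% to 15% and m from 25% to 100%, this runs from 75 × 0.05 × 0.25 = 0.9 to 75 × 0.15 × 1 = 11.3.
- True admission rate = f·h + (1−f) × 0.02. With f = 10% and h = 50%: 0.050 + 0.018 = 6.8%.
- Observed rate on the ITT denominator = f(1−m)h + f·m·h·r + (1−f) × 0.02. With m = 50%: 0.025 + 0.025r + 0.018, which is 4.3% at r = 0 and 6.8% at r = 1.
- With h = 20% instead: true 0.020 + 0.018 = 3.8%; observed at r = 0, 0.010 + 0.018 = 2.8%.
- Not admitted, h = 50%: true 93.2%. Observed on the ITT denominator: 0.10 × 0.5 × 0.5 + 0.90 × 0.98 = 90.7%. Excluding Indeterminates at r = 0: 90.7/95 = 95.5%.

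The observed admission rate on the ITT denominator cannot exceed the true one. The success rate can move either way, depending on how Indeterminates are handled.

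**The case against.** The best reply is that the rest of the protocol leans towards 9.7. FU may be by telephone only for clinical successes without adverse events or significant abnormalities, and must otherwise be in person (synopsis, Table 3-1 footnote e, Sections 8.1 and 11.10). Clinical failures fall under the in-person rule. Sections 12.4 and 12.6 describe TOC serology without exempting failures. Sites following 9.7 would collect everything, the study is descriptive, and Section 16.4 leaves missing-data handling to the SAP.

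Much of that stands and limits the consequence. It does not remove the conflict: the in-person rule governs how FU is held, while 9.4.1.2 speaks directly about this group and only encourages attendance. Missing-data rules cannot recover data that were never collected.

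Three stronger readings are tempting, and the documents do not support them:

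- *Admissions among failures become Indeterminate.* Not if already in the eCRF.
- *Failures with atypical pathogens leave micro-ITT.* Only if serology is their sole evidence. The protocol also does not define serologic response, or say that it requires a convalescent sample.
- *The size can be read from the 78% assumption.* A reader might take 22% of 75 = 16.5, suppose that about a third stop and miss FU, and quote 5/75 = 6.7 points. Day 4 response is programmatic and does not trigger stopping (Sections 11.5 and 13.2.1). The 22% includes Indeterminates, the 78% is assumed for the nafithromycin arms only, and the third has no source.

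**Conclusion.** The contradiction is real, and no other text resolves it. Following 9.4.1.2 creates a foreseeable risk of informative missing data in hospitalization, and in micro-ITT and ME membership where serology is the only pathogen evidence. A reader might infer that these data will go missing; the text shows only that they may.

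The effect is confined to secondary endpoints in a study without formal comparisons, although Section 16.2.3.2 does tabulate treatment differences in hospitalization with 95% intervals. The Day 4 primary endpoint, the sample-size statement and the TOC clinical outcome are unaffected.

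The size cannot be derived from the documents. The calculations above show mechanism and direction under assumed rates and are not estimates. The point should be fixed because prevention is cheap.

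**What to change.** Reconcile Section 9.4.1.2 with Section 9.7. State that every randomized subject who stops study drug for any reason, and has not withdrawn from the study, has convalescent serology collected at TOC and hospitalization status collected at FU.

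If telephone contact or a record check is to be accepted for FU hospitalization status in clinical failures, amend the in-person FU wording at the same time: the synopsis (study design and study visits), Table 3-1 footnote e, and Sections 8.1 and 11.10. Otherwise the change creates a new contradiction.

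The cost is protocol wording. The blood draw and the visit are already in the schedule.
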